3.3 Interventions

Paramedics will be trained in the use of the CCR prior to the start of the trial. We have conducted an Ottawa EMS CCR implementation pilot study and have designed our training program to address barriers identified in the pilot. The training entails one hour of education: 30 minutes of self-review of a teaching video addressing the background and scientific development of the CCR, and a 30-minute inclass teaching video reviewing the specific steps involved in using the CCR, complete with a demonstration and question and answer period with a certified trainer. Paramedics will be "certified" to clear the cervical spine by medical directive if they have: a) successfully completed the initial training sessions, and b) successfully completed (score of ≥80%) a written quiz. Paramedics failing the written quiz would be required to attend a remedial session and review all wrong answers with their certified trainer. Of note, Ottawa paramedics all successfully completed their training.

The stepped wedge trial will begin after paramedic training has been completed (see Figure 2). During the Usual Care phase, paramedics will complete the CCR data collection form for all eligible patients, but will continue to immobilize them all before transport to the receiving hospital. Once a community has crossed to the intervention CCR phase, paramedics will be permitted by medical directive to implement the CCR. Paramedics will then transport selected patients without immobilization according to the CCR. Although following the medical directive will be mandatory for paramedics, they will be encouraged and allowed to immobilize patients if they are uncomfortable with the CCR's recommendation to not immobilize them.

During the study set-up time period (Figure 2), each participating service will designate a local paramedic study champion. These individuals will be in close contact with staff at the Study Coordinating Centre and will receive further information about the study, the methodology and the implementation of the CCR. These individuals will be heavily involved in delivering the study training material at their particular location and will serve as a first point of contact throughout the implementation. Paramedics with questions about specific aspects of the CCR, or the application of the CCR for unusual scenarios will be able to communicate directly with a peer in an effort to promote adherence to the protocol.

Paramedics will be encouraged to ask questions during the training sessions, speak directly with their study champion, add comments to study forms, or communicate with study staff via the study website or through social media. These questions and concerns will be compiled and distributed back to study champions to disseminate to local staff. Staff at the study coordinating centre will regularly provide updates and reminders to study champions.

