Once on an ED stretcher, it is not unusual for these patients to remain fully immobilized for several hours until physician assessment and c-spine diagnostic imaging can be performed and interpreted. This consumes valuable time for physicians, nurses, and radiology technicians and distracts them from other urgent responsibilities. These delays compound the burden of our crowded Canadian EDs in an era when they are under unprecedented pressures. The median length of stay for a patient evaluated in the stretcher area is approximately 8-12 hours, whereas similar minor trauma victims arriving without immobilization can be evaluated and discharged in less than 4 hours.

The Canadian C-Spine Rule: We have derived, validated, and implemented the Canadian C-Spine Rule (CCR) to be used by physicians (7-9), triage nurses (10), and paramedics (11) in more than 40,000 alert and stable trauma patients. The CCR (Figure 1) directs that immobilization is unnecessary if the patient has no high-risk criteria, has at least one low-risk criterion, and can voluntarily rotate their neck 45' left and right. Physicians and nurses already use the CCR in the ED to safely remove immobilization devices without the need for imaging and with no documented adverse outcomes. We recently completed a pilot implementation study with Ottawa paramedics where selective patients were transported without immobilization. We have recruited 3,854 patients, and paramedics have identified all clinically significant injuries (100% sensitivity) without negative consequence when the CCR determined that immobilization was not required (68% specificity). Approximately 60% of immobilizations were avoided.

[figure not shown]
C-Spine Evaluation in Children: The NEXUS decision instrument for use in adults and children was validated in 2,160 children aged 8 to 17 (12) and identified all significant injuries. The CCR's performance was superior to that of the NEXUS decision instrument when prospectively compared in an adult population (13), but has yet to be implemented for use in children. A case-control study of children younger than 16 with c-spine injuries identified 8 risk factors for significant injuries, 7 of which are included in the CCR (14).

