2.3 Trial Design

The multicentre implementation of the CCR by paramedics is designed as a stepped wedge cluster randomized trial with three steps, involving a total of 13 Ontario EMS Services. Our 36-month study will consist of a 12-month set-up and training period (Year 1), followed by the stepped wedge trial (Year 2), and a 12-month period for study completion, analyses, and knowledge translation and exchange (see Figure 2). EMS services in each step will cross from the control condition (usual care) to the intervention condition (CCR implementation) at intervals of 3 months until all communities have crossed to the intervention. Data will be collected on all eligible patients in each EMS service for a total duration of 12 months.

Figure 2: Diagram of the Study and Stepped Wedge Design

-8			Months 1-9		Months 10-12	
ar 1		Study set-up	Paramedic			
Year		ePlatform progra	ePlatform programming for EMS data collection			
		Preparation of study material and site visits				
	Step	Months 1-3	Months 4-6	Months 7-9	Months 10-12	
ır 2	1 (4 EMS services)	Usual Care	CCR	CCR	CCR	
Year	2 (4 EMS services)	Usual Care	Usual Care	CCR	CCR	
	3 (4 EMS services)	Usual Care	Usual Care	Usual Care	CCR	
		Months 1-6		Months 7-9	Months 10-12	
ar 3		Study completion		Data cleaning	Reports and	
Year		Data linkage with ICES		Data analyses	manuscripts	
					writing; KTE	

Section 3. Methods: Participants, Interventions and Outcomes

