3.4.2 Measures of Patient Benefit

- a) Proportion of patients feeling comfortable (score ≤4 on a 10-point Likert scale) (co-primary outcome of interest),
- b) Proportion of patients with a pain score ≤4 on a 10-point Likert scale upon arrival at the Emergency Department (ED),
- c) Time from EMS arrival to ED discharge or admission to hospital,
- d) Patient radiation exposure (in millisieverts) from diagnostic imaging of the spine,
- e) Number of skin pressure injuries, and
- f) Number of missed clinically important c-spine injuries. A clinically important c-spine injury includes any injury other than the following defined unimportant injuries which require neither specialized treatment nor follow-up: isolated avulsion fracture of osteophyte, isolated fracture of transverse process not involving the body or facet joint, isolated fracture of the spinous process not involving the lamina, isolated simple compression fracture <25% of body height.

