3.6 Sample Size

Our sample size for this study is determined mainly by pragmatic considerations: we need a large number of sites from across Ontario to evaluate safety and generalizability of implementation in this multicenter setting, while accounting for between-site differences such as size and setting. Power calculations were carried out for the stepped wedge trial. Using data from a previous study in these communities, we expect approximately 600 patients per EMS service per year (or 150 patients per 3 month time interval). A total of 12 EMS services (7,200 patients) evaluated across 4 time intervals in a stepped wedge design will provide at least 90% power to detect minimally important differences of 10% in our two co-primary outcomes using two-sided tests at the 2.5% level of significance. In particular, for our primary outcome we will have >99.9% power to detect a minimally important absolute reduction of 10% in the proportion of patients immobilized assuming a control arm proportion of 100%. For our co-primary outcome we will have 90% power to detect a minimally important increase of 10% in the proportion of patients feeling comfortable assuming a conservative control arm proportion of 50%. In these calculations, we have assumed a commonly used intracluster correlation coefficient (ICC) of 0.05, added 2 EMS services to account for variation in the number of patients across sites, and a further 2 EMS services to account for potential attrition.

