5.1 Data Collection Methods

Once training of paramedic staff has been completed, paramedics will begin evaluating eligible patients with the CCR. Each time an eligible patient is assessed using the CCR, the paramedic treating that patient will complete and submit an electronic CCR (see Appendix 6. Paramedic Data Collection Form). The paramedic will also record patient-reported comfort level and pain level on this form. Staff at the study coordinating centre will receive the electronic EMS-completed CCR, as well as a copy of the Paramedic Care Record (ePCR). Study staff will review the paramedic documentation in order to assess compliance with the study protocol and application of the CCR. Information on patient age, gender, mechanism of injury, field time, offload time and immobilization status are contained in the ePCR and will be recorded from there (see Appendix 7. Study Data Collection Form).

We will link the information obtained from paramedic care records to provincial administrative databases housed at ICES. This linkage will allow us to obtain information related to the initial ED visit, c-spine diagnostic imaging, hospitalization, and subsequent ED/clinic/family physician visits within 30 days of injury.

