6.3 Harms

Adverse events will be classified according to the following definitions:

- 1. Protocol Deviations this category will include cases where the CCR was applied to the wrong patient population, or situations where the rule was applied inaccurately in the opinion of study staff. These will be included in DSMB reports for review at scheduled meetings.
- Adverse Events This category will include transport of patients without immobilization later determined to have an important cervical spine injury. This may include cases where the rule was applied incorrectly by the treating paramedic, or cases missed by the CCR. These cases will be reported to the DSMB and the REB for review and consideration.
- 3. Serious Adverse Events – This will include patients transported without immobilization who are later determined to have suffered a spinal cord injury with neurological deficit. If such a case was to ever occur, the study would immediately be stopped pending DSMB and REB ruling on whether the study can resume or not. Note: such a serious adverse event has never been observed in more than 36,000 patients evaluated with the CCR in various research studies this far.

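### The missed-injury outcome does not define a miss; on the only working definition it is zero by construction in Usual Care, and the rule's sensitivity is never estimated although the data are collected in both phases

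*Combined protocol and SAP*

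**What the plan says.** Section 3.3 has the form filled in before any service uses the rule: in Usual Care, "paramedics will complete the CCR data collection form for all eligible patients", while every such patient is still immobilized. In the CCR phase a paramedic who is uneasy about a negative result may immobilize anyway. Appendix 6 records the rule's result and any override. Appendix 7 records the rule's result, the study phase and actual immobilization as separate items. On injuries, 5.1 states: "This linkage will allow us to obtain information related to the initial ED visit, c-spine diagnostic imaging, hospitalization".

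The safety outcome in 3.4.2(f) is "Number of missed clinically important c-spine injuries". The section goes on to define which injuries are clinically important, but not what makes one missed. The nearest working definition is the adverse event in 6.3: "This category will include transport of patients without immobilization later determined to have an important cervical spine injury". Appendix B of the DSMB terms repeats it.

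Section 5.4 plans to express the intervention effect on each secondary outcome as an absolute difference, relative risk or odds ratio. It contains no accuracy analysis, and sensitivity is not among the outcomes in 3.4. The pilot's safety result in 2.1 was an accuracy result: "paramedics have identified all clinically significant injuries (100% sensitivity".

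**The concern.** If 3.4.2(f) takes its meaning from 6.3, two problems follow. First, nobody in Usual Care can have the event, because everyone there is immobilized. A relative risk or odds ratio against a control count of zero has no useful estimate, and the absolute difference can only be zero or unfavourable to the intervention, whatever the truth.

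Second, an injured patient whom the rule clears does not enter the outcome if that patient is in Usual Care or is overridden in the CCR phase. A low or zero count would then rest on at most half of the occasions on which the rule could have failed. The other half carries accuracy information at no added risk to patients and is not analysed. This matters for a trial meant to examine safety across diverse services. It matters also because patients are enrolled from age 8, while 2.1 says the rule has not yet been implemented in children.

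**Working it through.** **The plan's own total.** Section 3.6 gives "A total of 12 EMS services (7,200 patients) evaluated across 4 time intervals in a stepped wedge design", with "approximately 600 patients per EMS service per year (or 150 patients per 3 month time interval". 12 services × 4 quarters × 150 = 7,200, which matches.

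**Split by phase.** Services cross over "at intervals of 3 months until all communities have crossed to the intervention". Figure 2 shows 4 services per step, with 3, 2 and 1 CCR quarters.
- CCR: 4 × (3 + 2 + 1) = 24 of 48 service-quarters; 24 × 150 = 3,600 patients, 50%.
- Usual Care: 4 × (1 + 2 + 3) = 24 service-quarters, 3,600 patients.

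With no overrides, therefore, 50% of rule misses could be counted under the 6.3 definition. This is the design ceiling at equal volume per service-quarter. Ottawa's paediatric data lie outside this calculation.

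**Allowing for overrides.** Section 2.1 gives a pilot specificity of 68% and about 60% of immobilizations avoided.
- Rule-negative patients actually not immobilized: 60/68 = 88.2%, so about 12% overridden.
- Countable share: 0.50 × 0.882 = 44.1%.
- If 1% are injured and all of them are rule-positive, the rule-negative share is 0.99 × 0.68 = 67.3%, and the countable share is 0.50 × 60/67.3 = 44.6%.

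**The early review in 6.2.** The first two months are all Usual Care: 12 services × 2 months × 50 patients per month = 1,200, or 16.7% of 7,200. Adding them puts about 44% + 17% = 61% of rule misses under some form of review (67% with no overrides). The review produces no estimate or interval.

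**Precision of sensitivity.** Section 2.1 says under 1% have a c-spine fracture. It gives no rate for clinically important injury, so I assume 0.5% to 1%. With k injuries and no misses, the exact two-sided 95% lower limit is 0.025^(1/k).

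| Patients used | Injuries k at 0.5% and 1% | Lower limit |
|---|---|---|
| CCR half (3,600) | 18 and 36 | 81% and 90% |
| Both phases (7,200) | 36 and 72 | 90% and 95% |

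These limits take patients as independent and make no allowance for clustering by service.

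**The case against.** The strongest reply is that the exclusion is inferred. Section 3.4.2(f) does not say that immobilized patients cannot count, and 6.2 uses the idea of a missed injury more broadly. It plans to check the first two months, when all patients are immobilized, for injuries missed by the paramedics or by the rule itself. It also says that c-spine injuries in eligible patients will be monitored as information arrives. This stands. A reader might infer that the plan shuts Usual Care out of the outcome, or never looks there for rule misses; the documents support neither. What they show is an undefined term, one working definition that would exclude Usual Care, and a case check without an estimate.

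Nor is this the only safety event: 3.4.2(e) counts skin pressure injuries, and 6.3 has a separate category for spinal cord injury with deficit.

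A reader might take 44% as an upper limit. It is a projection from the pilot's average override rate. The ceiling is 50%, and the share falls below 44% if overrides concentrate in injured patients. A reader might also apply 44% to all injuries, giving 16 to 32 countable injuries and lower limits of 79% to 89%. That is not valid: 44% is a share of rule misses, and injured rule-positive patients in the CCR phase are immobilized and never countable under 6.3. The proper comparison is with the CCR half.

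Finally, the question in 2.2 concerns a strategy in which paramedic discretion has a place, and 2.1 reports that the rule is already validated. So counting harm under the strategy is legitimate and should stay. That does not make the count a substitute for rule accuracy, nor does it give the 5.4 comparison any content.

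**Conclusion.** The point holds as a gap in definition and analysis. Outcome 3.4.2(f) leaves a miss undefined. On the only working definition in the documents, the Usual Care count is zero by construction, the planned comparison is uninformative, and at most 50% of rule misses (about 44% on pilot figures) can enter the outcome. The 44% assumes equal service-quarters and the same override rate in injured as in other rule-negative patients.

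Using both phases doubles the injuries behind a sensitivity estimate. With no misses and an assumed 0.5% to 1% important injuries, the exact lower limit rises from 81%–90% to 90%–95%. The co-primary analyses are unaffected. This is an inexpensive improvement to the safety analysis, not a flaw in the design.

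**What to change.** In 3.4.2(f) and 5.4, define a rule miss as a CCR-negative result recorded by the paramedic in a patient with a clinically important injury in the linked data, in either phase and whether or not the patient was immobilized. Add to 5.4 the sensitivity and specificity of the recorded result, with exact confidence intervals, overall and by phase. Keep injury in patients not immobilized for transport as a separate harm count, reported descriptively for the CCR phase.

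The cost is some wording and one further two-by-two table, with no new data collection or change in care. There are limits to state:
- Usual Care results have no consequence for the patient and may be recorded less carefully, so the phases should be shown side by side.
- Linked data find only diagnosed injuries and may not grade each one to the 3.4.2(f) definition, for example by degree of compression. The plan should state the injury definition those data can support.
- Section 5.2 does not follow up eligible patients in whom the rule was not applied, so the estimates describe assessed and linked patients only.

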3.4 Outcomes

The outcomes of interest are divided into three categories: measures of patient and health system benefit, measures of patient benefit and measures of health system benefit.

3.4.1 Measures of Patient and Health System Benefit

a) proportion of patients transported with immobilization (primary outcome of interest)

3.4.2 Measures of Patient Benefit

- a) Proportion of patients feeling comfortable (score ≤4 on a 10-point Likert scale) (co-primary outcome of interest),
- b) Proportion of patients with a pain score ≤4 on a 10-point Likert scale upon arrival at the Emergency Department (ED),
- c) Time from EMS arrival to ED discharge or admission to hospital,
- d) Patient radiation exposure (in millisieverts) from diagnostic imaging of the spine,
- e) Number of skin pressure injuries, and
- f) Number of missed clinically important c-spine injuries. A clinically important c-spine injury includes any injury other than the following defined unimportant injuries which require neither specialized treatment nor follow-up: isolated avulsion fracture of osteophyte, isolated fracture of transverse process not involving the body or facet joint, isolated fracture of the spinous process not involving the lamina, isolated simple compression fracture <25% of body height.

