2.2 Objectives

The overall goals and impacts of this study are to improve patient care and health system efficiency and outcomes by allowing paramedics to assess eligible low-risk trauma patients with the CCR and selectively transport them *without* immobilization to the ED.

We conservatively estimate that, in Ontario, more than 60% of all eligible trauma patients (300,000 annually) could be transported safely and comfortably, without c-spine immobilization devices. This will significantly reduce patient pain and discomfort, EMS intervention times, and ED length of stay, therefore improving access to EMS and ED care. This could be achieved rapidly and with lower healthcare costs compared to current practices (possible cost saving of \$36 per immobilization, or \$10,656,000 per year).

In addition, this project will facilitate a new paradigm in prehospital research by integrating paramedics and patients actively into the research and knowledge translation process. It will offer the added benefits of consolidating a network of EMS research partners and of facilitating future collaborative projects. It will also make innovative use of data provided by the Institute for Clinical Evaluative Sciences (ICES) to streamline and decrease the cost of conducting prehospital research, and, with the help of our new OSSU partners, foster collaborative efforts to measure and possibly correct health inequities in prehospital care. Lastly, this project could lead to the use of the CCR by paramedics from across Ontario and Canada and to immediate health care benefits/savings on a national scale.

PICOT Question: Does allowing paramedics to assess selective low-risk trauma patients with the Canadian C-Spine Rule (CCR) and transporting them without immobilization result in significant and immediate health service benefits for patients, Emergency Medical Services, and Emergency Departments, in a safe, cost-effective manner?

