5.4 Statistical Methods

Analyses will be conducted at the level of individual patient data using generalized linear mixed effects regression with a random effect to account for clustering by EMS service, and fixed effects for treatment and time interval to account for the stepped wedge design. The primary and co-primary outcomes will be analyzed using binomial distribution with identity link and the effect of intervention will be expressed as absolute differences with 97.5% confidence intervals. Secondary outcomes will be similarly analyzed using binomial distribution and identity or logit link for dichotomous variables, normal distribution and identity link after log-transformation or gamma distribution and log-link for continuous variables with a skewed distribution, or Poisson or negative binomial distribution with log link for count variables. The effect of the intervention on each secondary outcome will be described using absolute difference, Relative Risk or Odds Ratio with 95% confidence interval. Subgroup analyses (described below) will be conducted by including interactions with time interval and treatment in the regression model.

Our **health economist** will perform a cost-effectiveness analysis from the perspective of the Ministry of Health and Long-Term Care. Trial data will be used to populate the relative costs and outcomes of the use of the CCR by paramedics with usual care (100% immobilization). Resource use will be collected during the trial and obtained from ICES, while unit costs will be obtained from appropriate Canadian

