6.2 Data Monitoring - Interim Analyses

The intervention period for this multi-centre study is fairly short - only 12 months long. Because of this, there are no interim analyses planned.

The number of c-spine injuries in eligible patients will be monitored as outcome information is available. We plan to obtain preliminary information on a small subset of study outcomes for safety assurance purposes before the first cluster of centres begin actively using the CCR. We will send the required information to ICES based on the first two months of enrollment following training (see Figure 2). Analysts at ICES will link our data at that time with the information available from the Ontario Health Insurance Plan (OHIP) database, as well as the Canadian Institute for Health — Discharge Abstract Database (CIHI-DAD). This will give us information on which cases had c-spine imaging performed, and of those, whether any c-spine injuries were identified. We will then review these cases to ensure that the CCR was applied appropriately and that no injuries were missed by either the paramedics, or the CCR itself.

The only situation that would trigger an immediate review to consider stopping the trial would be a situation where a spinal cord injury was sustained by an enrolled patient and believed to be a direct consequence of having transported a patient without immobilization resulting from the use of the CCR. In this case, we would notify the DSMB to review the available information and discuss their review and recommendations with the Steering Committee.

We would not consider a missed significant injury sufficient to warrant stopping the study as long as there was no consequence to the patient's safety and health i.e. not resulting in a spinal cord injury that was not already present before transport to the hospital. Any missed significant injury will be reported to both the DSMB and Research Ethics Board in a timely manner.

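### Missed c-spine injury is not defined, and a between-phase effect cannot give the upper bound on risk that the safety question needs

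*Combined protocol and SAP*

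**What the plan says.** Section 3.4.2(f) lists the "Number of missed clinically important c-spine injuries". It explains at length which injuries are clinically important, but not what makes one missed, and it names no denominator.

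Section 5.4 specifies regression with a random effect for EMS service and fixed effects for treatment and time interval. For secondary outcomes it states: "The effect of the intervention on each secondary outcome will be described using absolute difference, Relative Risk or Odds Ratio with 95% confidence interval". It mentions no exact or sparse-data method.

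Section 6.3, repeated in Appendix B of the DSMB terms of reference, has an adverse-event category for "transport of patients without immobilization later determined to have an important cervical spine injury". Nothing links it to outcome (f).

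Section 6.2 uses the word in a third place. It describes an early check, on the first two months of enrolment, that "no injuries were missed by either the paramedics, or the CCR itself".

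On design, section 3.3 says that usual-care paramedics complete the CCR form for all eligible patients "but will continue to immobilize them all before transport to the receiving hospital". Section 2.3 has services cross over every three months "until all communities have crossed to the intervention".

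On purpose, the PICOT question in section 2.2 asks about benefit "in a safe, cost-effective manner", and section 3.6 says that "we need a large number of sites from across Ontario to evaluate safety and generalizability of implementation in this multicenter setting".

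**The concern.** If outcome (f) is the section 6.3 event, usual-care patients cannot have it unless the protocol is broken, because they are all immobilized. A between-phase contrast then has a structural zero on one side. The quantity a reader needs is how large the risk could be among patients moved without immobilization, and the plan does not ask for it.

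Near-zero counts are the expected case. Section 2.1 reports that the pilot's paramedics identified every clinically significant injury among 3,854 patients. With so few events the size of the upper bound depends on the denominator and the interval method, and neither is fixed in advance. At stake is the trial's main safety statement. It could end as a model that does not converge, or as a fitted difference of zero that a reader takes for evidence of no added risk.

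**Working it through.** **Inputs.** Section 3.6 gives 12 services, four 3-month intervals and 150 patients per service and interval. The total 12 × 4 × 150 = 7,200 reproduces the plan's figure. The plan states no precision for missed injuries. Figure 2 has 4 services per step, so the CCR phase covers 4 × (3 + 2 + 1) = 24 of 48 service-intervals, or 24 × 150 = 3,600 patients. Months 10-12 hold 12 of those 24, or 1,800 patients. Section 2.1 gives about 60% of immobilizations avoided in the pilot; 0.60 × 3,600 = 2,160.

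**Relative risk and odds ratio.** Take the section 6.3 event and no usual-care events.
- If CCR-phase events fall in months 4-9, the likelihood keeps rising with the treatment coefficient and levels off without a finite maximum. In a Poisson log-link fit with 1 to 3 CCR-phase events, the log relative risk was 11.4 after 10 iterations and 26.4 after 25, with a standard error above 100,000.
- With a random service intercept (SD fixed at 0.5) and one event in each of the last three intervals, the log-link profile log-likelihood at coefficients 0, 4, 8, 12 and 20 was -25.585, -24.090, -24.043, -24.042 and -24.042. The logit link behaves the same way.
- If events fall only in months 10-12, the coefficient is not identified, because that interval's own effect absorbs them.

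**Absolute difference.** Let δ be the risk difference. Patients (usual care / CCR) number 1,200 / 600 in months 4-6, 600 / 1,200 in months 7-9 and 0 / 1,800 in months 10-12. The algebra below uses a Poisson approximation, holds risks at or above 0 and omits the service random effect, so it is not the full planned model.
- *Events only in months 10-12.* For δ ≥ 0, months 4-9 contribute -600δ - 1,200δ = -1,800δ. A negative δ also lowers the likelihood. The events are fitted by that interval's own effect, so the fitted δ is 0 however many there are.
- *One event in months 4-6, with CCR-phase risk r.* Months 4-6 contribute ln r - 600r - 1,200(r - δ) and months 7-9 contribute -1,200δ. The sum is ln r - 1,800r, and δ cancels. The maximum is at r = 1/1,800 = 0.056%, and every δ from 0 to 0.056% fits equally well. One event in months 7-9 gives the same expression.
- *The constraint decides.* If the usual-care risk in months 10-12, which no one observes, is also held at or above 0, a further -1,800δ enters and the fitted δ becomes 0.

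**Exact upper bounds for the CCR-phase risk.** With 0 events the two-sided 95% Clopper-Pearson upper limit is 1 - 0.025^(1/n). With x events it is the 97.5th percentile of Beta(x + 1, n - x).

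| Denominator | 0 events | 1 event | 2 events |
|---|---|---|---|
| 3,600 (all CCR phase) | 0.10% | 0.15% | 0.20% |
| 2,160 (not immobilized, at 60%) | 0.17% | 0.26% | 0.33% |

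**Clustering, zero events.** Design effect = 1 + (m - 1) × ICC, where m is the size-weighted mean service size, and effective n = n / design effect. For all CCR-phase patients (450, 300 or 150 per service), m = (450² + 300² + 150²) / 900 = 350. For those not immobilized (270, 180 or 90), m = (270² + 180² + 90²) / 540 = 210.

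| Assumed ICC | Design effect, 3,600 | Upper bound | Design effect, 2,160 | Upper bound |
|---|---|---|---|---|
| 0.001 | 1.349 | 0.14% | 1.209 | 0.21% |
| 0.005 | 2.745 | 0.28% | 2.045 | 0.35% |
| 0.01 | 4.49 | 0.46% | 3.09 | 0.53% |
| 0.05 | 18.45 | 1.87% | 11.45 | 1.94% |

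Only 0.05 comes from the plan (section 3.6, for the co-primary outcomes). It is probably too high for an event this rare.

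**The case against.** The strongest reply is that the plan already has most of what is needed. Sections 6.2 and 6.3 send each missed injury to the DSMB and the ethics board. Section 6.3 contains a workable event. Section 5.4 works on individual patients and allows an absolute difference, which with no usual-care events comes close to a CCR-phase risk. On this view only a cross-reference is missing.

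Much of that stands. A reader might infer that the documents hold two rival definitions of outcome (f). They do not: the section 6.2 sentence concerns a single early check before any service uses the CCR, while section 6.3 itself speaks of cases missed by the rule. The definition gap is mainly a missing link. Nor would it be right to say that safety goes unmonitored.

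A reader might also infer that the identity-link model always reports zero after a missed injury. That holds for events confined to months 10-12. For months 4-9 it depends on how an unobserved risk is constrained.

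The reply does not supply a named denominator or an interval method for near-zero counts, and it does not make the relative measures estimable. Case review answers whether an event occurred. It does not say how large the risk could be when none did.

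**Conclusion.** The point stands as a change that should be made, limited to this outcome. Outcome (f) lacks a definition of missed and a denominator. The prescribed between-phase effect is not estimable on the relative scales and is poorly determined on the absolute scale, given the section 6.3 event and adherence to usual care. The result worth reporting is an upper bound. With no events it is 0.10% to 0.17% under independence, and 0.14% to 0.35% at assumed ICCs of 0.001 to 0.005; at the plan's co-primary ICC of 0.05 it approaches 2%.

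These figures assume equal service volumes, 60% not immobilized, complete capture and linkage, and no Ottawa children in the denominator. The identity-link algebra omits the service random effect. It supports the statement that the difference is poorly determined, not any particular interval or coverage figure. Nothing here affects the sample size or the co-primary analyses.

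**What to change.** In section 3.4.2(f), define missed by the event in section 6.3 and Appendix B of the DSMB terms of reference.

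In section 5.4, take this outcome out of the between-phase models. Report the number of events in CCR-phase patients as a proportion of (i) those transported without immobilization and (ii) all CCR-phase patients, each with a Clopper-Pearson 95% interval. Add a sensitivity interval for clustering over a stated ICC range, since a handful of events cannot yield an estimate, and list events by service.

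State whether the Ottawa children (section 3.1), who have no usual-care phase, are in the denominator. Report how many patients lacked a form or ICES linkage, because section 5.2 rules out tracing cases in which the rule was not used.

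The cost is a few sentences and a small analysis on data already planned. The drawback is that two intervals must be shown, because Clopper-Pearson assumes independence. Sensitivity of the rule and injury risk among rule-negative patients could be added, but are optional.
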